### **6.4.2 Sample Size Considerations**

This was a pilot study and no a prior sample size calculation was completed.

### **6.4.3 Planned Analyses**

#### **6.4.3.1 Primary Analyses**

For the primary outcome, we will compare scores on the self-efficacy for providing diabetes education before and after training among the individuals that complete the training.

#### **6.4.3.2 Secondary Objectives Analyses**

For GDM knowledge scores, we will compare scores before and after training for the overall diabetes knowledge test and for each of the subscales associated with the content of the 4 modules among the individuals that complete the training.

For Diabetes Attitudes scales, we will compare scores before and after training on each of 3 subscales (patient autonomy, value of tight control, importance of specialized training) among the individuals that complete the training.

For Intention to Recommend Diabetes Prevention Measures, we will compare scores before and after training among the individuals that complete the training.

To provide preliminary validation for the new self-efficacy scale, we will report correlations between the self-efficacy for providing diabetes education measure and the General Self Efficacy Scale and Patient Teaching Motivation Questionnaire. We will also report internal reliability statistics (Cronbach's alpha) for the self-efficacy for providing diabetes scale, Diabetes attitudes scale subscales, and Intention to Recommend Diabetes Prevention Measures.

We will report the number of individuals who complete the pretest, access each of the training modules, and complete the post test.

#### **6.4.3.3 Analysis of Subject Characteristics**

Descriptive statistics

Age mean (SD)

Race/ethnicity (n/%)

Education (n/%)

Specialty (n/%)

#### **6.4.4 Other**

##### **6.4.4.1 Subsets and Covariates**

Will compare baseline statistics on individuals who complete and do not complete training

##### **6.4.4.2 Handling of Missing Data**

Individuals who do not complete the post assessment will not be included in the pre-post score comparison.

# 7 - Trial Administration

## 7.1 Ethical Considerations: Informed Consent/Accent and HIPAA Authorization

This study will be conducted in accordance with the ethical principles that have their origin with the Declaration of Helsinki.

### Protection of Human Subjects

- **Risks to Human Subjects:**

#### *1a) Human Subjects Involvement, Characteristics and Design:*

Eligible participants will be recruited for prospective data collection. Human subject involvement is essential in testing the proposed intervention. We will recruit 100 participants who self-report that they care for women who have gestational diabetes.

#### *1b) Study Procedures, Materials, and Potential Risks*

We will collect data from survey measures before and after module collection. Individual progress through pre and post assessments and all 4 assessments will be tracked by a self-generated anonymous identifier.

Risks of our study are minimal. Any identifiers collected for reimbursement of participants will be collected and stored separately in a REDCap database and is not linked to study answers.

- **Adequacy of Protection against Risks:**

#### *2a) Informed Consent and Assent:*

Participants will read a brief consent information sheet and then indicate if they would like to participate in the study with a yes or no answer.

#### *2b) Protections against Risks:*

Data are stored securely and collected anonymously.

#### *2c) Vulnerable Subjects*

This study does not recruit participants from vulnerable groups

- **Potential Benefits to Participants:**

Participants in the intervention arm will receive education and support which may improve their ability to take care of women with GDM and prevent future type 2 diabetes. There is no direct benefit for participants in the usual care arm.

- **Importance of Knowledge to be Gained:**

There are many potential benefits to the population of low-income women with GDM, healthcare providers and society in terms of knowledge to be gained. The online modules can be adapted to various education settings in the future.

### **Inclusion Plans for Women and Minorities:**

Individuals will be recruited with an attempt to have representation across gender and race and ethnicity. Given that we will be recruiting individuals involved in maternal-child healthcare, we anticipate that the majority of the sample will be female based on the composition of this workforce.

### **Inclusion Plans for Children:**

All individuals in the study will be at least 18 years of age as these must be individuals who are employed to care for women with GDM.

## **7.2 Institutional Review Board (IRB) Review**

This study will be approved by the Washington University institutional review board. This IRB reviews studies annually or as often as the research team submits modifications.

## **7.3 Subject Confidentiality**

Data will be stored in REDCap and Qualtrics with study identifiers only. There will be no link between identifiers collected for compensation and self-generated identifier for the study.

## **7.4 Deviations/Unanticipated Problems**

Adverse events will be reported to the IRB in the required time frame through submission of an adverse event reporting form.

## **7.5 Data Collection**

Data will be collected in the following ways

- 1) Qualtrics survey forms: participants will complete at baseline and after completion of online modules
- 2) Retention will be tracked by having individuals enter a self-generated identifier for the pre and post assessments and prior to entering each module.

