# 5 - Study Design

## 5.1 General Design Description

All healthcare professionals will undergo the same procedures. After reading the instructions/what to expect page, participants will first create a personal ID code that will allow their responses to be linked, but protect their identity. Next, they will decide if they would like to participate in the research study. If they elect to participate in the research, they will complete questionnaires related to GDM knowledge, both general self-efficacy and self-efficacy to provide diabetes education, teaching motivation, intention to recommend postpartum diabetes screening, and diabetes attitudes. They will also complete a demographics questionnaire. Next, all participants will complete an approximately 4-hour online GDM training at their leisure. The online training will be composed of 4 modules covering the following topics: 1) GDM Disease and Diagnosis, 2) Practical nutrition and exercise for women with GDM, 3) Blood sugar monitoring and medication for women with GDM, 4) Future Diabetes - risk, screening, and prevention.

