Items for each survey will be selected from previously validated measures and/or created by the PI. Items will be selected at the PI's discretion. All surveys and responses will be housed on Qualtrics. Participants will enter/create their unique personal ID before both survey sessions and before each education module. Participants may elect to complete the education training, but decline the option to participate in research.

If both the pre-assessment surveys and the post-assessment surveys are completed within 3 months, participants will be eligible to provide their information to be entered to win a \$40 Visa gift card. This identifiable information will only be collected to adhere to WashU institutional tax guidelines. This information will be collected using REDCap and will be stored separately from the research data.

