### **6.3.4 Recruitment, Enrollment and Retention**

Modules are hosted online. Information about the availability of the modules will be distributed via email through multiple professional organizations to reach clinical staff providing care for women with GDM. Contacts at the following organizations will be emailed with a brief information form including a link to the modules: Nurse Family Partnership, MU Extension, St. Louis Regional Health Commission, St. Louis Integrated Health Network, Association of Women's Health, Obstetrics and Neonatal Nurses, National Association of Community Health Workers, National Association of Community Health Centers, Missouri Nurses Association, Generate Health, the Missouri Diabetes Shared Learning Network, Missouri Primary Care Association, American Public Health Association, and St. Louis community college community health worker and nurse training programs. Modules are eligible for nursing continuing education credits (1 credit per completed module) through Washington University. Information about the study with optional pre- and post-training assessments will be provided on the home page for the modules. Individuals will be asked if they agreed to participate in the study with a single question prior to completion of the

pre assessment. Individuals who complete the pre-assessment will receive a code to enter the first module and then a different code at the end of each module to enter the next module, and finally the post-assessment. The codes will be used to ensure individuals access all modules prior to completion of the post-assessment. Individuals completing modules within 3 months are eligible for drawing for a \$40 Visa gift card.

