## **6.4 Statistical Method**

### **6.4.1 Statistical Design**

We plan a pre-post analysis of individual's scores on multiple continuous measures. For normally distributed data, a paired T test is planned. For non-normally distributed data, a Wilcoxon paired signed rank test is planned.

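### Does linking every pre-post pair through one self-generated ID, with no matching rule, put the results at risk?

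*Combined protocol and SAP*

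**What the plan says.** Section 5.1 sets up the link: "participants will first create a personal ID code that will allow their responses to be linked, but protect their identity". It adds: "Participants will enter/create their unique personal ID before both survey sessions and before each education module". Section 7.5 uses the same code for retention: "Retention will be tracked by having individuals enter a self-generated identifier for the pre and post assessments and prior to entering each module". Section 7.1, item 1b, repeats that progress is followed through this anonymous identifier, and Section 7.3 deliberately keeps the compensation data unconnected to it.

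Section 6.3.4 describes a separate set of codes: "Individuals who complete the pre-assessment will receive a code to enter the first module". A different code follows at the end of each module. Their stated purpose is sequence: "The codes will be used to ensure individuals access all modules prior to completion of the post-assessment". They are not described as person-specific.

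The analyses need the link. Section 6.4.1 says "For normally distributed data, a paired T test is planned", with a signed rank test otherwise. Section 6.4.3.1 says "we will compare scores on the self-efficacy for providing diabetes education before and after training among the individuals that complete the training". Section 6.4.3.2 does the same for knowledge, attitudes and intention, and adds: "We will report the number of individuals who complete the pretest, access each of the training modules, and complete the post test". Section 6.4.4.1 compares baseline data of those who do and do not complete training. Section 6.4.4.2 leaves people without a post-assessment out of the pre-post comparison. It does not mention a post-assessment that was completed but cannot be matched, or an ID that appears on more than one record.

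**The concern.** A paired analysis is only as good as its pairing. Participants make up the code, work at their own pace, and may have to recall it weeks later. The compensation data cannot rescue a lost link, and neither the quarterly review (7.6), the internal audits (7.11) nor the continuing-education records (7.7) are described as holding a second key. Three harms seem possible:

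- A forgotten ID loses the pair, and with it some precision.
- A duplicated ID could join one person's post-assessment to another person's baseline.
- A finisher who cannot be matched could be counted as a non-completer in the Section 6.4.4.1 comparison.

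With no written rule, unclear records might also be settled by someone who can see the scores. A second anonymous code looks like a cheap remedy, since the study already issues codes.

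**Working it through.** The plan states no figure to reproduce: Section 6.4.2 says no sample size calculation was made. The only input from the documents is 100 recruits (Section 5.3.1). Everything else here is an assumption: 60 completers; an unusable ID at the post-assessment for e = 2%, 5% or 10%; and, for a second key, a loss rate q of 20% or 50%, independent of ID errors.

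1. **Precision with one key.** Pairs lost = 60 × e = 1.2, 3, 6. The confidence interval for mean change widens by 1/√(1 − e) − 1:
   - e = 2%: 1.0%
   - e = 5%: 2.6%
   - e = 10%: 5.4%

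2. **Precision with two keys.** The unmatched share is u = e × q.
   - q = 20%: u = 0.4%, 1.0%, 2.0%; widening 0.2%, 0.5%, 1.0%.
   - q = 50%: u = 1.0%, 2.5%, 5.0%; widening 0.5%, 1.3%, 2.6%.
   - If the same people fail on both keys, the figures return to those in step 1 and nothing is gained.

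3. **False pairs.** Mean change over a set of pairs equals mean post score minus mean baseline score. If two completers' records are swapped, both means stay the same, so the estimated change is unchanged; only its variance and rank-based results can move. The estimate shifts only when the wrong baseline comes from someone outside the paired set. One such error with baselines 1 SD apart (assumed) shifts the mean by 1/60 = 0.017 SD. Assuming equal SDs and a pre-post correlation of 0.5, the SD of change equals the baseline SD, and the 95% half-width is about 1.96/√60 = 0.25 SD.

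4. **Duplicate IDs.** No ID format is given in the text. For evenly spread IDs with K possible values, the expected number of coinciding pairs among 100 people is (100 × 99/2)/K = 4,950/K. That is 4.95 for three digits, 0.495 for four and 0.005 for six.

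5. **Completers against non-completers.** Section 6.4.4.1 speaks of completing training, which the ID entries before each module can show, so an error confined to the post-assessment has no effect. Suppose instead that completion were judged by a matched post-assessment, with e = 5%. Three of 60 finishers would join 40 true non-completers: 3/43 = 7.0%. A true baseline difference of 0.5 SD would shrink by 0.5 × 0.070 = 0.035 SD. The 95% half-width for 57 against 43 is 1.96 × √(1/57 + 1/43) = 0.40 SD.

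6. **Retention counts.** The number of post-assessments submitted can be counted without matching them to baselines, apart from repeat submissions.

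7. **Redundancy.** The ID is entered at two surveys and before four modules, six times in all. A mistyped entry can be set beside up to five others.

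**The case for a change.** The best case for a change is that the absence of a rule is a fact, whatever the error rate. Section 6.4.4.2 covers only people with no post-assessment, so someone must decide what to do with duplicates and near-matches, and nothing says this happens before scores are seen. Section 5.1's wording about entering or creating an ID before each session does not clearly rule out making a new one. Because people may take the modules while declining the research, module traffic alone may not show how far research participants got. Error rates could also be higher than assumed above. With 70 completers and 20% or 30% failure, 70 pairs fall to 56 or 49, and the standardised change detectable with 80% power (two-sided 5%) rises from 0.34 to 0.38 or 0.41.

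Most of these facts stand, but they do not make the plan wrong. Even the 30% case costs precision in a study that calls itself a pilot and makes no power claim. The instructions page that precedes ID creation is not in the text and may give a reproducible recipe, which would put errors near the low end.

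The second key is also less simple than it looks. The code issued after the pre-assessment is the gate to module 1. Asking for it while turning away nobody who has lost it would remove that gate unless a separate code were kept. Nor can entry dates settle a clash between two baselines that both precede the post-assessment; using them could create the false pairs they are meant to prevent. If collection is over, as the past tense in the Synopsis (Study Duration) and Section 6.1.2 suggests, no key can be added.

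**Conclusion.** No change to the plan follows. The dependence on one re-entered ID is real, and so is the silence on duplicate and unmatched records, but following the plan as written produces no wrong result. An unmatched post-assessment cannot enter a paired test, so its exclusion is already implied. Repeated entry of the ID helps resolve typing errors, and training completion can be read from module entries. On assumed error rates of 2% to 10% the interval widens by 1.0% to 5.4%. The benefit of a second key depends on the two keys failing in different people and on collection still being open.

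The single key is a fair trade for anonymity in an exempt pilot. The rest is a gap that a careful analyst fills: match before looking at scores, leave ambiguous records unmatched, and report how many there were. The conclusion would weaken if many IDs proved unusable or the ID had a very short format, and the documents do not settle either point.

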## **7.6 Data Quality Assurance**

Data will be reviewed by the study coordinator on a quarterly basis to assess completeness and protocol adherence.

## **7.7 Study Records**

Regulatory: Incentive log, Delegation log, Team member HRPO and GCP training and certification, IRB approval memo, Protocol, Qualtrics surveys, Data collected by CME office on entry/completion of interactive questions in modules

## **7.8 Access to Source**

Data needed to provide compensation will be stored in a secure REDCap database. Survey answers will be stored by study ID in Qualtrics.

## **7.9 Data or Specimen Storage/Security**

Data will be stored in REDCap and Qualtrics and exported into SPSS for analysis.

#### **7.10 Retention of Records**

Records will be retained for 7 years after the completion of the study. They will be destroyed in a HIPAA compliant manner under the supervision of the principal investigator at that time. Any records that need to be moved will be done under the supervision of the principal investigator.

#### **7.11 Study Monitoring**

The team will conduct internal audits quarterly for quality assurance and reporting purposes.

#### **7.12 Data Safety Monitoring Plan**

The intervention will be provided in addition to standard of care. We will not be administering medication through the study and the study protocol will not change clinical decision making. I do not anticipate adverse events or circumstances related to study procedures that would pose a safety hazard to participants. The PI, members of the research team and the WUSM Human Research Protections Office will monitor the study for safety. In the unlikely event of an adverse event, the PI, in collaboration with relevant personnel, will take the appropriate action and report the event to the Human Subjects Research Protections Office (HRPO). While we do not anticipate any circumstances will arise that would compromise the safety of participants, should such an event occur, it will be reported to the PI immediately and research will be suspended until appropriate procedures are in place to allow the continuation of the study.

#### **7.13 Study Modification**

Study modifications will be submitted to the IRB when the need for changes arise. Changes to the protocol will only be implemented after appropriate IRB approval is received.

#### **7.14 Study Discontinuation**

The study will be discontinued if enrollment targets are not reached by 2 years or if there are adverse events directly attributed to the interaction between the patient and the community health worker.

#### **7.15 Study Completion**

Completion of the primary outcome collection is anticipated to be 8/2022

#### **7.16 Conflict of Interest Policy**

The study team members have no financial conflicts of interest with this study. Any conflicts of interest that arise during the conduct of the study will be reported to the IRB immediately.

#### **7.17 Funding Source**

This study is funded by NICHD K23HD096214

#### **7.18 Publication Plan**

There are no requirements for review prior to publication from the funders. The PI is primarily responsible for publishing study results.

# Appendix

## Pre- and post-assessment surveys

**\*GSES and PTMQ to be used to assess convergent validity of the SEPDE and only administered in the pre-assessment**

### General Self-Efficacy Scale (GSE)

Items: 10

Scoring:

	Not at all true	Hardly true	Moderately true	Exactly true
All questions	1	2	3	4

Questions:

1. I can always manage to solve difficult problems if I try hard enough
2. If someone opposes me, I can find the means and ways to get what I want
3. It is easy for me to stick to my aims and accomplish my goals.
4. I am confident that I could deal efficiently with unexpected events.
5. Thanks to my resourcefulness, I know how to handle unforeseen situations.
6. I can solve most problems if I invest the necessary effort.
7. I can remain calm when facing difficulties because I can rely on my coping abilities.
8. When I am confronted with a problem, I can usually find several solutions.
9. If I am in trouble, I can usually think of a solution
10. I can usually handle whatever comes my way.

### Physician Teaching Motivation Questionnaire (PTMQ)

Items: 4

Scoring: Answers on a Likert scale from 0 to 4. Zero represents “does not apply at all” and 4 represents “fully applies” for all questions.

Note: word “unit” changed to “opportunity” in question 1 to better reflect experience of our participants.

[figure not shown]
Questions:

1. I look forward to my next teaching opportunity most of the time.
2. I enjoy my teaching most of the time.
3. During my teaching, I am completely in my element.
4. Teaching enriches my job.

## **Self-Efficacy for Providing Diabetes Education (SEPDE)**

Items: 15

Scoring: Please select a whole number that represents your degree of confidence with each of the statements below. Response scale:

### **Statements related to specific components of diabetes education:**

**I feel confident that I can...**

1. Teach a woman how to check her blood sugar.
2. Talk to women about healthy culturally relevant food choices and alternatives.
3. Help women change their diet from unhealthy food choices to healthy food choices.
4. Help women plan meals to keep their blood sugar in a good range.
5. Help a woman find an exercise she can do safely during pregnancy.
6. Recognize when a woman's blood sugars are too high and she needs to speak to the doctor.
7. Recognize low blood sugar symptoms and tell a woman how to treat this effectively without over treating.
8. Tell a woman what steps she can take to prevent diabetes after pregnancy.
9. Describe diabetes screening recommendations after a pregnancy with gestational diabetes.

### **Statements related to overall ability in teaching:**

**I feel confident that I ....**

10. Can ask for the support I need to provide high quality education to patients with gestational diabetes.
11. Am able to identify and address challenges that may make providing diabetes education difficult.
12. Can try out different ways to overcome learning challenges and help the patient understand, even when a patient struggles with the concepts I am teaching.
13. Am as good as others with my level of training at teaching patients about their gestational diabetes.
14. Can set realistic goals with my patients to reach their blood sugar targets (for example, I can help a patient recognize that drinking soda raises blood sugar and set a goal to substitute soda with another non-caloric drink).
15. Can help my patients make a plan to meet their diabetes care goals.

Scoring: Calculate mean score from all components (and mean score of subscales if load on more than one factor).

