## 4.3 Secondary Objectives (if applicable)

Conduct a preliminary validation of a newly developed measure to assess self-efficacy to provide diabetes education

Assess adoption of the modules and retention in the overall training

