## **5.2 Outcome Variables**

### **5.2.1 Primary Outcome Variables**

The primary outcome is change in score on the self-efficacy to provide diabetes education questionnaire before and after completing the 4 module training. This was a newly developed measure

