### **5.2.2 Secondary and Exploratory Outcome Variables (if applicable)**

- 1) Score change on Diabetes Knowledge test (overall and on subscores tied to content of each of 4 modules)
- 2) Score change on 3 subscales of the Diabetes Attitudes Scale-3
  - Patient Autonomy
  - Value of Tight Control
  - Importance of Specialized Training
- 3) Score change on Intention to Recommend Diabetes Prevention Measures Questionnaire (Newly Developed)
- 4) Percent of individuals accessing each module and pre-and post assessments
- 5) Validation of Self Efficacy for Providing Diabetes Education Scale
  - Correlation of baseline scale scores and General Self Efficacy Scale and Physician Teaching Motivation Questionnaire
- 6) Internal reliability statistics for all scales (Cronbach's alpha)

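### Does the SEPDE scoring rule need a planned factor analysis that section 6.4 does not contain?

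*Combined protocol and SAP*

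**What the plan says.** The SEPDE (protocol Appendix) has 15 items in two blocks. Items 1 to 9 stand under "Statements related to specific components of diabetes education" and items 10 to 15 under "Statements related to overall ability in teaching". The scoring line reads "Calculate mean score from all components (and mean score of subscales if load on more than one factor".

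The scale carries the primary outcome (section 5.2.1): "The primary outcome is change in score on the self-efficacy to provide diabetes education questionnaire before and after completing the 4 module training". Section 4.3 adds a secondary objective: "Conduct a preliminary validation of a newly developed measure to assess self-efficacy to provide diabetes education".

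The analyses that serve this objective are listed in two places:

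- Section 5.2.2: "Correlation of baseline scale scores and General Self Efficacy Scale and Physician Teaching Motivation Questionnaire", followed by Cronbach's alpha for all scales.
- Section 6.4.3.2: "we will report correlations between the self-efficacy for providing diabetes education measure and the General Self Efficacy Scale and Patient Teaching Motivation Questionnaire", and "We will also report internal reliability statistics (Cronbach's alpha) for the self-efficacy for providing diabetes scale".

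The Appendix states that the two comparison questionnaires are there to assess convergent validity and are given at the pre-assessment only. Section 6.1.3 points to a survey code book for reliability and validity information; that code book cannot be identified in the text reviewed. Nowhere does section 6.4 name a factor analysis, its sample, a rule for the number of factors, or an SEPDE subscale.

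**The concern.** The scoring rule contains a condition that only an analysis of item structure can settle, and the statistical section plans no such analysis. Alpha does not count factors: with 15 items it can be high when the items measure two things. A correlation of the total score with another questionnaire says nothing about structure either. Two dimensions are plausible from the layout alone, since confidence in specific diabetes topics and confidence in teaching generally need not move together.

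Two things would be at stake. A high alpha might be presented as support for a single scale that is really two, with one correlation per comparison questionnaire hiding the difference. Conversely, a factor analysis added later could use a rule for the number of factors chosen after seeing the data, and some rules split a scale that truly has one factor. Both would touch the validation of the instrument behind the primary outcome.

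**Working it through.** The documents give no loading, factor correlation or factor-analysis figure, so there is nothing to reproduce. The check has two parts.

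**1. Can the planned statistics show the number of factors?**

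From the Appendix: 15 items in blocks of 9 and 6. Assumed: equal loadings L, and a correlation phi between the two block factors. Items within a block then correlate L², and items in different blocks L² × phi. The sum of the item correlation matrix is

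S = 15 + L² × (9×8 + 6×5) + L² × phi × (2×9×6) = 15 + 102 L² + 108 L² phi,

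and standardized alpha = (15/14) × (1 − 15/S).

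| L | phi | S | alpha |
|---|---|---|---|
| 0.7 | 0 | 64.98 | 0.824 |
| 0.7 | 0.3 | 80.86 | 0.873 |
| 0.7 | 0.5 | 91.44 | 0.896 |
| 0.7 | 1 (one factor) | 117.90 | 0.935 |
| 0.6 | 1 (one factor) | 90.60 | 0.894 |

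For two factors with phi from 0 to 0.5, alpha runs from 0.76 to 0.85 at L = 0.6 and from 0.87 to 0.93 at L = 0.8. An alpha near 0.9 therefore fits either structure.

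The total-score correlation can also mask a difference. Suppose a comparison questionnaire correlates 0.1 with block 1 and 0.5 with block 2 (L = 0.7, phi = 0.3). The block sums have variances 9 + 72 × 0.49 = 44.28 and 6 + 30 × 0.49 = 20.70. The correlation with the total is (0.1 × √44.28 + 0.5 × √20.70) / √80.86 = 0.33.

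So this part of the concern is right: the planned statistics do not settle dimensionality.

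**2. Which planned result depends on the answer?**

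| Planned result | Where | Needs the number of factors? |
|---|---|---|
| Pre-post change in SEPDE score | 5.2.1, 6.4.3.1 | No; the mean of all items is always computed |
| Baseline correlations with the two questionnaires | 5.2.2, 6.4.3.2 | No; they use the scale score |
| Cronbach's alpha for the SEPDE | 5.2.2, 6.4.3.2 | No |
| SEPDE subscale means | Appendix only | Yes, but no listed outcome or analysis uses them |

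Only the last row is conditional. Much of the implied step is also settled by context. The validation correlations use baseline scores, the comparison questionnaires exist only at baseline, and the two item headings name the candidate subscales. What is truly open is the rule for the number of factors.

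**How much could that rule matter?** Simulation with 100 respondents (the recruitment target in section 5.3.1), 15 normally distributed items and 2,000 samples per setting gave:

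- True single factor: counting eigenvalues above 1 suggests two or more factors in 88%, 9% and 0% of samples at L = 0.6, 0.7 and 0.8. Parallel analysis retains more than one factor in 0%.
- Two factors correlated 0.5: parallel analysis finds exactly two in 93%, 99% and 100%.
- Two factors correlated 0.7: it finds two in 23%, 42% and 66%. A separate run of 500 samples gave 29% and 46% at L = 0.6 and 0.7.

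The 88% figure requires both weak loadings and a rule that the plan never mentions.

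**The case for a change.** The best argument for a change is that the plan's authors foresaw more than one factor, or the conditional clause would not be there. Section 6.4.3.2 spells out the subscales for the knowledge test and the attitude scale but is silent on the SEPDE. Sections 5.2.1 and 6.4.3.1 do not say in so many words that the primary score stays the 15-item mean if the items split. Naming the method would take one paragraph and no new data, and calling the study a pilot excuses a small sample more readily than it excuses an unstated method.

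Part of this stands. The method is not written down, and a report that cited alpha as proof of a single dimension would be wrong. But the plan makes no such claim; it promises convergent validity and internal consistency, and its analyses deliver those.

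On the primary score, the Appendix gives one unconditional score, and section 5.2.1 speaks of a score in the singular, so the 15-item mean is the natural reading. A change confined to one block would be diluted: 0.5 points on items 1 to 9 alone gives 9 × 0.5 / 15 = 0.30 on the total, and on items 10 to 15 alone 6 × 0.5 / 15 = 0.20. That describes what an overall mean measures and is not an error in it.

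A prespecified factor analysis would also gain little in one plausible case. Both blocks ask about confidence and overlap in content (meal planning and diet in items 3 and 4, goals and plans in items 14 and 15), so a high factor correlation is quite possible. There, parallel analysis with about 100 respondents would often report one factor, the same reassurance for which alpha is blamed.

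**Conclusion.** No change is needed. The concern is right that alpha and total-score correlations cannot show whether the SEPDE is one scale or two, and that the factor step implied by the scoring line is not described in section 6.4. It is a gap in detail that an analyst fills sensibly: examine the baseline item loadings, say which rule was used, and treat any subscales as exploratory.

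The effect is limited to optional subscale means that no outcome or analysis relies on. The primary pre-post comparison, the baseline correlations and alpha can all be computed as planned and mean what the plan says they mean.

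The overlap in alpha (0.82 to 0.90 for two factors at loading 0.7 with phi from 0 to 0.5, against 0.89 to 0.94 for one factor at loadings 0.6 to 0.7) rests on assumed loadings and correlations. So do the simulated rates, which also assume normally distributed items. The conclusion does not depend on those values, because it follows from which results use the subscales. It does assume that the primary score is the mean of all 15 items, as the Appendix indicates, and that the report does not offer alpha as evidence of a single factor.
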